## **Study design**

This study was a prospective, single-center, open-labeled, randomized controlled trial designed to evaluate the safety and efficacy of ER combined with EDN for treating lower limb PAD. Patients who meet the following criteria were randomly assigned to the group of ER alone or ER combined with EDN. Subjects in the control group were treated with ER including PTA, DCB, and/or stenting, and patients in the ER+EDN group were treated with EDN from distal iliac artery to proximal superficial femoral artery before ER.

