## **Sample size**

1 site, 20 subjects.

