## **Statistics and Analysis**

All continuous data are presented as mean  $\pm$  standard deviation (SD) or median with interquartile range. Categorical data are reported as numbers and percentages. Paired *t*-test and Wilcoxon signed-rank test were used to compare parameters at baseline and the 6-month follow-up. Student's *t*-test and Mann-Whitney *U* test were used to compare parameters between the two groups. When multiple follow-ups were analyzed, one-way repeated-measures ANOVA along with Bonferroni correction were used. Differences in categorical data between the two groups were analyzed using the chi-square test. *P* < 0.05 was considered statistically significant. All statistical analyses were performed using SPSS (version 22.0, SPSS, Chicago, USA) and GraphPad Prism 8 (GraphPad Software, San Diego, California).

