**Visit 3 (7±2 days):**

The visit was considered 7±2 days after surgery. Blood routine examination, renal function, liver function, blood electrolyte, catecholamine, glycated hemoglobin, angiotensin II, aldosterone, insulin, glucagon, homocysteine, blood pressure assessment, blood glucose, ankle-brachial index (ABI), transcutaneous partial pressure of oxygen (TcPO2), foot sensory threshold measurement, VUS microcirculation detection, pain NRS score were performed. Drug use and complications.

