**Visit 4 (1month±7 days):**

The visit was considered 1 month ±7 days after surgery. Blood routine examination, renal function, liver function, coagulation function, blood lipid, catecholamine, glycated hemoglobin, angiotensin II, aldosterone, insulin, glucagon, homocysteine, blood pressure assessment, blood glucose, ankle-brachial index (ABI), transcutaneous partial pressure of oxygen (TcPO2), foot sensory threshold measurement, VUS microcirculation detection, Ruthe were performed rford scale, Wagner scale of diabetic foot ulcer, pain NRS score, painless walking distance PFWD examination, drug use and complications.

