**Visit 5 (3 months±7 days):**

The visit was considered 3 months ±7 days after surgery. Blood routine examination, renal function, liver function, coagulation function, blood lipid, blood electrolyte, catecholamine, glycosylated hemoglobin, angiotensin II, aldosterone, insulin, glucagon,

homocysteine, blood pressure assessment, blood glucose, ankle-brachial index (ABI), transcutaneous partial pressure of oxygen (TcPO2), foot sensory threshold measurement, VUS microcirculation detection, blood pressure assessment, blood pressure assessment, blood pressure assessment. Rutherford scale, Wagner scale of diabetic foot ulcer, pain NRS score, painless walking distance PFWD examination, drug use and complications.

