#### **Visit 6 (6 months±7 days):**

The visit was considered 6 months ±7 days after surgery. Blood routine examination, renal function, liver function, coagulation function, blood lipid, blood electrolyte, catecholamine, glycosylated hemoglobin, angiotensin II, aldosterone, insulin, glucagon, homocysteine, blood pressure assessment, blood glucose, ankle-brachial index (ABI), transcutaneous partial pressure of oxygen (TcPO2), foot sensory threshold measurement, VUS microcirculation detection, blood pressure assessment, blood pressure assessment, blood pressure assessment. Rutherford scale, Wagner scale of diabetic foot ulcer, pain NRS score, painless walking distance PFWD examination, color Doppler ultrasound, computed tomography angiography (CTA), drug use and complications.

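### The time-course analysis is a one-way repeated-measures ANOVA, which drops every patient lacking a value at any analysed visit; a mixed model would keep the observed data

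*Combined protocol and SAP*

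**What the plan says.** All references are to the combined protocol and SAP.

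- **Method for several visits.** Statistics and Analysis states: "When multiple follow-ups were analyzed, one-way repeated-measures ANOVA along with Bonferroni correction were used". It names no other method for this purpose.
- **Other tests in the same section.** Baseline and 6 months are compared by a paired t-test or signed-rank test. The two groups are compared by a t-test or Mann-Whitney test. The primary endpoint, stated after the exclusion criteria, is ABI improvement at 6 months, so these tests cover it.
- **Schedule.** ABI, TcPO2 and NRS are taken at screening (Visit 1) and at four follow-ups: "The visit was considered 7±2 days after surgery", "The visit was considered 1 month ±7 days after surgery", "The visit was considered 3 months ±7 days after surgery" and "The visit was considered 6 months ±7 days after surgery". Rutherford category is listed at screening and at 1, 3 and 6 months, but not at day 7.
- **Size and arms.** The Sample size section reads "1 site, 20 subjects". Patients are "randomly assigned to the group of ER alone or ER combined with EDN"; no allocation ratio is given.
- **Not stated.** The plan has no rule for missed visits or withdrawals, no imputation, no definition of analysis sets and no dropout allowance. It does not say which parameters or visits enter the ANOVA, or what happens to a value taken outside a visit window.

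**The concern.** Classical repeated-measures ANOVA needs a complete row for each patient. A patient who attends screening, day 7 and month 1 and then withdraws contributes nothing to it, although three values were observed. A patient who misses only month 1 is lost in the same way.

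Two things are at stake. The first is efficiency: with 20 patients in two arms, few need to be incomplete before the analysis rests on a handful per arm. The second is representativeness. Enrolment runs to Rutherford VI, so attendance may plausibly depend on how the limb is doing. Deleting incomplete patients then also discards the early values that help to explain why they left, and the time course describes mainly those who did well.

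The plan could also report 6-month change in two different sets of patients. The paired test keeps anyone with baseline and 6-month values, while the ANOVA drops any of them who missed an intermediate visit.

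**Working it through.** The sample size of 20 comes without power, effect size, SD or dropout, so there is no figure in the plan to reproduce. The check concerns how the method behaves and how many patients it would keep.

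**1. Does the method delete whole patients?** Data were simulated for 10 patients at 5 time points (screening plus four follow-ups), giving 10 × 5 = 50 values. A one-way repeated-measures ANOVA has error df (n − 1)(t − 1) = 9 × 4 = 36. With one value deleted, the ANOVA routine stopped and reported unbalanced data. It ran only after the whole patient was removed, with error df 8 × 4 = 32 on 45 values. Four observed values were therefore discarded for one absent value. A mixed model on the same incomplete data used all 49. That fit gave a boundary warning, because the data were simulated without between-patient variation; it serves here only to count the values used.

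**2. How many patients remain?** Inputs:

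- n = 20 (Sample size section).
- v = 4 follow-ups for ABI, TcPO2 and NRS, and v = 3 for Rutherford category (Visits 3 to 6).
- m = probability that a follow-up is missed. The documents give none; 2% to 15% is assumed.
- Misses are assumed independent, and the screening value is assumed present for everyone.

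Formulas:

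- Expected complete cases: 20 × (1 − m)^v.
- Expected patients with a 6-month value, who can enter the paired test: 20 × (1 − m).
- Chance that at least one of 20 is incomplete, v = 4: 1 − (1 − m)^80.
- Share of observed follow-up values discarded, v = 4: 80(1 − m) are observed and 80(1 − m)^4 are kept, so the share is 1 − (1 − m)^3.

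| m | (1 − m)^4 | Complete of 20, v = 4 | Complete of 20, v = 3 | Have 6-month value | At least one incomplete | Observed values discarded |
|---|---|---|---|---|---|---|
| 2% | 0.922 | 18.4 | 18.8 | 19.6 | 80% | 6% |
| 5% | 0.815 | 16.3 | 17.1 | 19.0 | 98% | 14% |
| 10% | 0.656 | 13.1 | 14.6 | 18.0 | about 100% | 27% |
| 15% | 0.522 | 10.4 | 12.3 | 17.0 | about 100% | 39% |

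If allocation is 1:1 (an assumption), the v = 4 figures per arm of 10 are 9.2, 8.1, 6.6 and 5.2.

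**3. Which way could the bias go, and is it peculiar to the ANOVA?** Suppose patients with a smaller early gain are more likely to be absent later. The complete cases are then selected for larger gains. Two patterns differ:

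- *Withdrawal, so that months 3 and 6 are missed together, with no other misses.* Patients with a 6-month value are exactly the complete cases. The paired test and the ANOVA use the same patients and give the same 6-month gain, so the bias is shared in full.
- *Scattered misses.* Some patients have a 6-month value but lack an earlier one. The ANOVA drops them and the paired test keeps them, so the sets differ and only part of the bias is shared.

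The documents give no ABI standard deviation, no correlation between visits and no dropout mechanism, so no magnitude follows from them.

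**The case against.** The strongest reply is that this is a supporting analysis in a 20-patient study of preliminary efficacy. The primary 6-month ABI comparison does not pass through the ANOVA, no missing-visit rate is given, and with complete attendance nothing is lost. The plan names two software packages, and some software switches to a mixed model when values are missing. The time-course result might therefore not suffer the deletion in practice.

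Much of this stands: the reach is limited and the loss depends on attendance. It does not justify leaving the method as written. Even at 2% missed per visit, the chance that some patient is incomplete is 80%, and the plan should not leave the choice of method to a program default.

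A reader might infer three stronger points that the documents do not support:

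- *That the primary result is compromised.* It is not compromised by this deletion. The paired test keeps anyone with baseline and 6-month ABI, even if the intermediate visits were missed.
- *That attending outside the day-7 window removes a patient.* The plan sets a window but nowhere excludes a late or early value. Only an absent measurement causes deletion.
- *That the 6-month gain would be inflated by a definite percentage.* Any such figure rests on an assumed true gain, variance, correlation and dropout strength. Part or all of the bias would also appear in the paired test, which a change to the ANOVA does not cure.

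**Conclusion.** The point holds for the time-course analysis only. The one method named for several follow-ups keeps only patients with a value at every analysed visit, and the plan gives no alternative for the rest.

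Assuming independent misses over four follow-ups, about 16, 13 or 10 of 20 patients would remain at 5%, 10% or 15% missed per visit. For Rutherford category, with three follow-ups, the figures are about 17, 15 or 12, if it is analysed this way at all. The rates are assumptions, and the exact loss depends on which parameters and visits are entered.

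Bias towards patients who did well is possible if missingness depends on earlier response; its size is not established. This is a cheap improvement to a stated method.

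**What to change.** In Statistics and Analysis, replace the one-way repeated-measures ANOVA for the continuous repeated measures (ABI, TcPO2 and NRS) with a linear mixed model that uses every observed visit. Specify:

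- group, visit (categorical) and group-by-visit as fixed factors, or a separate fit within each arm; a visit-only mean pooled over two randomised arms would not be sound;
- a simple covariance structure suited to 20 patients;
- a small-sample method for the degrees of freedom;
- Bonferroni correction, kept for the visit contrasts;
- a report of the number of patients contributing at each visit, by arm.

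The cost is wording only: no visit, measurement or patient is added. The downside is small. The model relies on its covariance assumption and on missingness being explained by observed values. It does not address missing 6-month values in the paired and two-group tests.

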## **The inclusion criteria:**

- (a) eligible subjects aged 18-75 years;
- (b) clinically confirmed PAD in the lower extremities;
- (c) Rutherford category II-VI.

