## **The exclusion criteria:**

- (a) thrombolytic therapy performed within 30 days;
- (b) patients who had undergone vascular bypass surgery before this study;
- (c) allergy or contraindication of antiplatelet drugs, anticoagulants, thrombolytic drugs and contrast agents,;
- (d) patients with obvious bleeding tendency, coagulation dysfunction, hypercoagulability and blood system diseases;
- (e) serious liver and kidney diseases;
- (f) history of hemorrhagic stroke within last month or ischemic stroke or transient ischemic attack within 2 weeks;
- (g) pacemaker implants;
- (h) patients who are pregnant, breast-feeding or planning pregnancy;
- (i) expected survival < 24 months.

**The primary endpoint** was the improvement of ABI at 6-month post-procedure.

**The secondary endpoints** included transcutaneous oxygen pressure (TcPO2), Rutherford category, numerical rating scale (NRS) score and safety.

**Safety endpoints** was the occurrence of trial-related adverse events that occurred during this trial. Possible adverse or serious adverse events during surgery: femoral artery stenosis, femoral artery dissection, thromboembolism (stroke or TIA), pus, hematoma at the puncture site, arteriovenous fistula requiring blood transfusion and/or surgical treatment, and other "serious" adverse events during the trial.

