## **Study process**

### **Visit 1 (Subject Screening):**

During this visit, cases are selected. Collect demographic data of patients, record patients' past medical history and medication, record vital signs, and collect patients' general physical examination. Blood pressure assessment, Rutherford scale, Wagner scale of diabetic foot ulcer, pain NRS score, painless walking distance PFWD examination, electrocardiogram examination, anklebrachial index (ABI), transcutaneous partial pressure of oxygen (TcPO2), foot sensory threshold measurement, thromboelastography (TEG), VUS microcirculation detection, and target vessels were performed. Color Doppler ultrasound and computed tomography angiography (CTA) were used to sign informed consent for patients who met the initial criteria. Blood biochemical tests were performed, including blood routine, liver function, kidney function, urine routine, blood lipids, coagulation function, blood electrolytes, catecholamines, glycosylated hemoglobin, angiotensin II, aldosterone, insulin, glucagon, homocysteine, blood glucose.

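### Rutherford category is an ordered secondary endpoint, but the only between-group rule worded for categorical data is the order-blind chi-square test; name the Mann-Whitney U test for it

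*Combined protocol and SAP*

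**What the plan says.** The secondary endpoints, listed after the exclusion criteria, include "Rutherford category, numerical rating scale (NRS) score and safety". Entry is limited to "Rutherford category II-VI", so the scale is graded and has five levels at entry. It is recorded at screening ("Blood pressure assessment, Rutherford scale, Wagner scale of diabetic foot ulcer, pain NRS score") and again at 1, 3 and 6 months (at 6 months: "Rutherford scale, Wagner scale of diabetic foot ulcer, pain NRS score").

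Statistics and Analysis is the whole statistical plan. It recognises two data types, continuous and categorical. For the second it says "Categorical data are reported as numbers and percentages" and, between groups, "Differences in categorical data between the two groups were analyzed using the chi-square test". A separate sentence offers Student's t-test and the "Mann-Whitney *U* test were used to compare parameters between the two groups". It links no test to a named endpoint and gives no rule for ordered data.

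The form of the primary endpoint is stated: it "was the improvement of ABI at 6-month post-procedure". The Rutherford endpoint has no such statement, either of level versus change or of a visit.

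**The concern.** An endpoint called a category falls most literally under the categorical rule. The Pearson chi-square test treats the levels as unordered labels. With five levels it spreads its sensitivity over (2 - 1) x (5 - 1) = 4 degrees of freedom, although the effect of interest is a shift in one direction. In 20 patients that is a poor use of the data.

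If the analyst instead treats Rutherford as a parameter, the rank test applies and nothing is lost. The plan does not say which is meant. Power on a secondary endpoint is therefore at stake under one reading. If the matter stays open until the data are in, the analyst can also choose between two tests after seeing both results.

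**Working it through.** **Inputs from the documents.** Total 20 subjects (Sample size); two randomised groups (Study design); five levels at entry (inclusion criteria); significance at P < 0.05 (Statistics and Analysis). The plan gives no power or effect figure for Rutherford category, so there is none to reproduce.

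**Assumptions, none of them in the documents.** 10 per arm; two-sided testing; the 6-month level compared; proportional odds, meaning that at every cut of the scale the treated arm's cumulative odds of a milder category equal the control odds times the odds ratio (OR). The number of levels in use at 6 months and the control distribution are also assumed, and are varied below.

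**Step 1: does chi-square use the order?** Take 1/2/3/3/1 versus 4/3/2/1/0. Chi-square gives P = 0.380 in the true column order and in two shuffled orders. Mann-Whitney (normal approximation) gives 0.052 in the true order and 0.437 and 0.756 in the shuffled ones. Chi-square does not use the order, whatever the assumptions.

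**Step 2: one constructed table, to show what can happen.** Mildest to most severe, 5/3/1/1/0 versus 1/2/3/2/2. Column totals are 6, 5, 4, 3, 2, so expected counts per arm are 3, 2.5, 2, 1.5, 1.
- Chi-square = 2 x (4/3 + 0.25/2.5 + 1/2 + 0.25/1.5 + 1/1) = 2 x 3.10 = 6.20 on 4 df, P = 0.185.
- Mid-ranks are 3.5, 9, 13.5, 17, 19.5. Rank sums are 75 and 135 (total 210), so U = 75 - 55 = 20 against 50 expected. Exact P = 0.021.

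Both tests look at the same difference, but they fall on different sides of 0.05.

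**Step 3: power by simulation.** Pearson chi-square on non-empty columns, against exact Mann-Whitney with mid-ranks. Share lost = 1 - (chi-square power / rank-test power).

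| Levels in use (control %) | OR 2 | OR 4.5 | OR 8 |
|---|---|---|---|
| Three (35/40/25) | 9.0 v 8.7%: none | 25.3 v 28.9%: 12.5% lost | 42.6 v 48.4%: 12.0% lost |
| Four (40/30/20/10) | 7.3 v 10.5%: 30.5% lost | 19.1 v 29.4%: 35.0% lost | 32.5 v 45.0%: 27.8% lost |
| Five (20/25/25/20/10) | 5.9 v 11.5%: 48.7% lost | 19.8 v 40.0%: 50.5% lost | 36.8 v 62.9%: 41.5% lost |
| Seven (10/15/20/20/15/10/10) | 3.5 v 12.7%: 72.4% lost | 12.1 v 41.9%: 71.1% lost | 26.4 v 66.9%: 60.5% lost |

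The four-level row uses 4,000 runs per cell and the others 20,000 (Monte Carlo standard error 0.35 points at 50%). Over three five-level control distributions the loss is 42-59% at ORs 2 to 8, and falls to 23-27% at OR 20. A skewed three-level control (50/30/20) loses 4% or less. The normal-approximation rank test has more power in coarse tables, so losses measured against it are larger: 45-63% with five levels and 27-33% with three.

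**Step 4: choosing after seeing the data.** With no true difference, over three, five, six and seven levels at 10:10 and 12:8, chi-square alone rejects in 2.0-4.9% of trials and exact Mann-Whitney alone in 3.3-4.7%. One or the other rejects in 5.9-7.1% (6.4-7.6% with the normal approximation). Further three-level checks gave 5.0-5.5%, and one five-level run with the normal approximation gave 7.7%. The range is about 5-8%. At OR 4.5 with five levels, the tests disagree on significance in about 25% of trials: only Mann-Whitney is significant in 22-23%, only chi-square in 2%.

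**The case against.** The strongest reply is that the documents never assign Rutherford category to chi-square. A reader might infer that they do, and so that the trial has chosen a test that costs it half its power. The text does not support that. The visit schedule lists Rutherford as a scale beside the NRS score, and Mann-Whitney U is available for parameters. On that reading nothing is lost. This stands: the defect is two possible readings, one of which is inefficient.

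The size of the loss is also uncertain. Five levels are given at entry only; nothing is said about the spread at 6 months. With three levels and exact P values the loss is 13% at most, and none at OR 2. This stands too, and is why no single figure should be quoted.

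A reader might also infer that the two tests could give contradictory findings, or that false positives are seriously inflated. Neither follows. The tests can differ about significance but do not point to opposite effects, and the excess over 5% is at most about 3 points on one secondary endpoint.

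Two further replies stand in part. No endpoint has a named test, so the gap is wider than Rutherford; but only here does one reading lead to a test that discards the order. And the within-group sentence does name baseline and 6 months for parameters, so a visit is implied if Rutherford counts as one. It does not settle the between-group comparison, or level versus change.

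**Conclusion.** The point holds as a minor one. An ordered secondary endpoint has no assigned test, and the only between-group rule worded for categorical data ignores order. That much rests on the text and on a property of the chi-square test.

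The size is conditional. If chi-square is used, with 10 per arm and proportional odds assumed, about 40-60% of rank-test power is lost with five levels in use at ORs 2 to 8, roughly 28-35% in the four-level case examined, and little or none with three levels and exact P values. If the choice is left open, the false-positive rate for this endpoint is about 5-8%.

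The primary ABI analysis is untouched. Twenty patients give low power for modest shifts under either test: with five levels, 11-12% at OR 2 even with Mann-Whitney.

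**What to change.** In Statistics and Analysis, state that Rutherford category at 6 months is compared between groups with the Mann-Whitney U test already in the plan, using an exact P value, and not with the unordered chi-square test. State also whether the 6-month level or the change from baseline is compared.

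The cost is one or two sentences. The test is already listed and the scale is already recorded at screening and at 6 months, so no visit, measurement or patient is added. If only about three levels turn out to be in use, the gain in power is small or nil, but the open choice of test is still closed.

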## **Study process**

### **Visit 1 (Subject Screening):**

During this visit, cases are selected. Collect demographic data of patients, record patients' past medical history and medication, record vital signs, and collect patients' general physical examination. Blood pressure assessment, Rutherford scale, Wagner scale of diabetic foot ulcer, pain NRS score, painless walking distance PFWD examination, electrocardiogram examination, anklebrachial index (ABI), transcutaneous partial pressure of oxygen (TcPO2), foot sensory threshold measurement, thromboelastography (TEG), VUS microcirculation detection, and target vessels were performed. Color Doppler ultrasound and computed tomography angiography (CTA) were used to sign informed consent for patients who met the initial criteria. Blood biochemical tests were performed, including blood routine, liver function, kidney function, urine routine, blood lipids, coagulation function, blood electrolytes, catecholamines, glycosylated hemoglobin, angiotensin II, aldosterone, insulin, glucagon, homocysteine, blood glucose.

